## 2.3 EXPLORATORY OBJECTIVES AND ASSOCIATED ENDPOINTS

Exploratory Objectives	Associated Exploratory Endpoints
1. Describe the efficacy of VGX-3100, administered alone or in combination with imiquimod, at Week 74 and/or Week 96 as measured by reduction in the surface area of the qualifying  vulvar lesion(s), in subjects without a complete resolution at Week 48	1. Percent reduction in the cumulative surface area of the acetowhite vulvar lesion(s) as determined by the quantitative analysis of standardized pre-biopsy photographic imaging of the qualifying lesion (s) at Week 74 and/or Week 96 compared to baseline  . Results will be classified as: no clinically significant lesion resolution (reduction in lesion area of 0-25%), partial lesion area resolution (>25% and <100% reduction), and complete lesion resolution (no visible lesion).
2. Describe the long term efficacy of VGX-3100, alone or in combination with prior imiquimod, as measured by histologic regression of vulvar HSIL	2. Proportion of subjects with no evidence of vulvar HSIL on histology (i.e. biopsies or excisional treatment) at Week 74 for subjects who receive 5 doses of VGX-3100 and at Week 96 for subjects who receive 6 doses of VGX-3100.
3. Describe the long term efficacy of VGX-3100, alone or in combination with prior imiquimod, as measured by virologic clearance of HPV-16/18	3. Proportion of subjects with no evidence of HPV-16/18 in vulvar tissue samples at Week 74 and/or Week 96.
4. Evaluate tissue immune responses to VGX-3100, and VGX-3100 with imiquimod, as measured in vulvar tissue samples	4. Assessment of pro-inflammatory and immunosuppressive elements in tissue 
5. Describe virologic clearance of HPV-16/18 from non-vulvar anatomic locations	5. Proportion of subjects who have cleared HPV-16/18 on specimens from non-vulvar anatomic locations without surgical intervention (inclusive of cervix, oropharynx, vagina and intra-anus) at Week 48 compared to baseline
6. Describe association of microRNA (miRNA) profile, previous vulvoscopy, and HPV testing results with Week 48 histologic regression	6. Vulvoscopy, HPV test results (vulvar swab and vulvar tissue) and miRNA profile (Day 0, Week 15 and 48) in conjunction with histologic regression of vulvar HSIL at Week 48 visit
7. Describe patient reported outcomes (PRO) for subjects treated with VGX-3100 and VGX-3100 with imiquimod	7. PRO endpoints will be obtained at Day 0 prior to first dose, Weeks 4, 12, 24 after dosing, and at Weeks 15, 27, 48, 52, 74, and Weeks 96, and 100 as applicable.

8. Describe the humoral and cellular immune response of VGX-3100 administered alone or in combination with imiquimod, post dose 3, post dose 4, and after additional dosing
	
8a. Levels of serum anti-HPV-16 and anti-HPV-18 antibody concentrations at baseline, Weeks 15, 27, 48, 74, and 96 visits 8b. Interferon-<math>\gamma</math> ELISpot response magnitudes at baseline and Weeks 15, 27, 48, 74 and 96 visits

9. Determine the long term efficacy of VGX-3100 alone or in combination with imiquimod with respect to histopathologic regression of vulvar HSIL or virologic clearance of HPV-16/18 in vulvar tissue
	
9. Proportion of subjects with no histologic evidence of vulvar HSIL or no evidence of HPV-16/18 at Week 74 and 96 in vulvar tissue samples (i.e. collected via biopsy or excisional treatment)

### 3. STUDY DESIGN

HPV-201 is a Phase 2, randomized, open-label efficacy study of VGX-3100 (DNA plasmids encoding E6 and E7 proteins of HPV types 16 and 18) administered by IM injection followed by EP delivered with CELLECTRA™ 2000 alone or in combination with imiquimod in adult women with histologically confirmed vulvar HSIL associated with HPV-16/18. Approximately 36 subjects will be enrolled. Twenty-four subjects will receive VGX-3100 alone and 12 subjects will receive VGX-3100 and topical imiquimod treatment. The Version 3.0 protocol amendment halts enrollment of the VGX-3100 with topical imiquimod study group. All subjects who have already been enrolled into the VGX-3100 with imiquimod study group will continue with all study visits per protocol, but no further participants will be enrolled into this group.

Subjects are randomized in a stratified manner according to (a) recurrent disease at screening (0 vs. 1 or more recurrences), (b) multifocal disease (1 vs. 2 or more lesions at screening), (c) Body Mass Index (BMI) category ( $\leq 25$  vs.  $>25$  kg/m^2) on Day 0, and (d) age category ( $<45$  years vs.  $\geq 45$  years) on Day 0.

To be eligible for the study, subjects must sign consent to participate and have a vulvar punch biopsy/biopsies of approximately 4 mm with lesion remaining, and photographs of the acetowhite vulvar lesion(s) at the time of screening. In the case of multifocal disease, the two lesions that potentially contain the most advanced disease, as judged by the Investigator, should be chosen for biopsy using vulvoscopy and documented using standardized high resolution photography with a digital single-lens reflex (SLR) camera on the case report form. Biopsy slides will be sent to a PAC for evaluation prior to enrollment. In order to be eligible for enrollment, the PAC must assign the diagnosis of vulvar HSIL based on the biopsy sample(s). Subjects must also have a vulvar specimen test positive for HPV genotype 16 and/or 18 to be eligible for participation in the study.

To assess quality of life and related impacts on subjects, PRO instruments will be provided and will include the Short Form Health Survey version 2 (SF-36v2™), the EQ-5D-5L (EuroQoL Research Foundation), WOMAN-PRO (WOMen with vulvar Neoplasia) Clinical Trial Version 2.0 and two additional PRO questions assessing quality of life after surgery or biopsy.

The total duration of the study is up to 10 weeks for the screening period, and 100 weeks for the treatment and follow-up periods. Amendment 5.0 reduces the study duration to 78 weeks for subjects not reaching the Week 78 visit at the time of the amendment

### 3.1 TREATMENT REGIMENS

All eligible subjects who consent to participate in the study will receive four doses of 6 mg of VGX-3100 administered by IM injection followed by EP. The first dose will be administered as soon as possible following confirmation of the HSIL diagnosis, HPV-16/18 status and all other eligibility criteria but no more than 10 weeks following collection of the subject's biopsy specimen used for diagnosis by the PAC.

Each dose of VGX-3100 will be administered in a 1 mL volume IM (deltoid preferred site, or the anterolateral quadriceps as an alternate site) followed immediately by EP with the CELLECTRA™ 2000 device. [Figure 1 \(Appendix A\)](#) shows the original study visit schedule, in which study subjects will receive at least 4 doses of VGX-3100 and potentially a 5th and 6th dose depending upon their disposition with regard to histologic and lesion area changes. [Figure 1a](#) shows the revised visit schedule per Protocol Amendment 5.0. In both schedules, the first dose will be administered on Day 0, the second at Week 4, the third at Week 12, and the fourth dose will be administered at Week 24. Subjects with no HSIL at Week 48 (Subgroups A and B) will receive 4 doses. Subjects with HSIL at Week 48, who have a reduction in lesion size or no increase in lesion size from baseline (Subgroups C or D), may receive a fifth dose at Week 52 per the judgment of the Investigator.

With Amendment 5.0, subjects will complete the study at Week 78 and will not be offered a 6th dose. Subjects who were beyond Week 78 at the time of IRB approval of Amendment 5.0, will return for their final visit at their next scheduled timepoint as outlined in [Table 1](#). Subjects must sign the IRB-approved informed consent document for Amendment 5.0 prior to the initiation of procedures for their final study visit.

Imiquimod treatment – Participants who have been enrolled in the VGX-3100 with imiquimod study group will continue with study visits per protocol, but no further participants will be enrolled into this study group. Subjects randomized to the VGX-3100 with imiquimod study group will apply imiquimod 5% cream to the vulvar lesion beginning in the evening on Day 0, and will continue to apply treatment three times per week for 20 weeks (inclusive of administration in the evening of VGX-3100 dosing). Subjects unable to tolerate imiquimod treatment may reduce their dosing frequency, and will document their use on the imiquimod dosing log provided.

### 3.2 EFFICACY ASSESSMENT

The efficacy assessment will be based upon histopathology. Visualization of a normal appearing vulva by visual inspection with vulvoscopy is insufficient evidence to confirm disease regression. Disease regression will be based on histopathologic assessment at Week 48, 74, and at Week 96 for subjects reaching Week 96 prior to Amendment 5.0 or for whom that is the final visit. Subjects will be monitored during the course of the study by vulvoscopy. Lesion(s), defined as areas that stain acetowhite, will be assessed and photographed during vulvoscopy at Screening, Day 0, and Weeks 4, 12, 27, 48, 74, and at Week 96 for subjects who have reached this timepoint prior to Amendment 5.0 or for whom this is the final visit. Using standardized high resolution digital photographic imaging, vulvar lesion(s) will also be quantitatively measured at Screening, Day 0, and Weeks 48, 74, and at Week 96 for subjects who have reached that timepoint prior to Amendment 5.0 or for whom that is their final visit.

Biopsies obtained as part of the study at Screening will be from the region of most advanced disease as judged by the Investigator, and must be approximately 4 mm in

length. Visible lesion must remain after screening biopsy to ensure measurement on study. A qualifying lesion is defined as a vulvar lesion which is confirmed to be HPV-16 and/or HPV-18 positive and have histologically confirmed vulvar HSIL by the PAC at screening.

The decision process following results of the Week 48 biopsy are described in [Figure 2](#) and are as follows: At Week 48, the subject will undergo repeat vulvar punch biopsy/biopsies of the same lesions as study start, from the region of most advanced disease based upon the judgment of the Investigator (see [Table 2](#) for Minimally Required Biopsy Procedures).

If after evaluation of biopsy tissue by the PAC there is no evidence of HSIL ([Figure 2](#), Subgroups A or B), the subject will continue to Week 74 for vulvoscopy, and biopsy of the same lesion(s) as study start.

If after evaluation of the biopsy tissue HSIL remains, but there is a reduction in lesion size or no increase in lesion size from baseline ([Figure 2](#), Subgroups C or D), the Investigator has the option to give the subject a 5th dose of VGX-3100 at Week 52, and the subject will continue on study with vulvoscopy and biopsy at Week 74. Alternatively, the Investigator may choose to treat the subject with surgical or standard treatment, and the subject will continue on study without further biopsy.

The decision process following results of the Week 74 biopsy for subjects who completed this visit prior to Amendment 5.0 are described in [Figure 3 \(Appendix B\)](#) for the original study design. The evaluation process following results of the Week 74 biopsy under Amendment 5.0 are described in [Figure 3a](#) and are as follows: At Week 74, the subject will undergo repeat vulvar punch biopsy/biopsies of the same lesion as at study start Investigator(see [Table 2](#)). If, after evaluation of Week 74 biopsy tissue by the PAC, there is no evidence of HSIL (Subgroups A or B), the Investigator will use their clinical judgment regarding follow-up care of the subject (not part of study activities).

If, after evaluation of the biopsy tissue HSIL remains, but there is a reduction in the qualifying lesion(s) size or no change in lesion size from baseline (Subgroups C or D), the subject will receive further standard of care treatment (not part of study activities) per the Investigator's judgment.

The decision process for subjects who are beyond Week 78 at the time of IRB approval of Amendment 5.0 can be found in [Appendix C](#). These subjects will complete the study at their next scheduled visit as outlined in [Table 1](#). Subjects must sign the IRB-approved informed consent document for Amendment 5.0 prior to the initiation of procedures for their final study visit.

In the event of worsening disease prior to the end of the study (i.e., Subgroup E), the subject will receive surgical treatment per the Investigator's judgment and will continue on study with vulvoscopy, but without further study treatment or biopsy. In the event of worsening disease at the final visit, the subject will receive standard of care treatment (not part of study activities) per their treating physician. If wide excision is conducted at or prior to the subjects last on site visit, the sample obtained will be sent to the PAC for evaluation. For a finding of carcinoma, subjects will receive surgical treatment, and be discontinued from study treatment. The event will be reported as an SAE per [section 7.1.4](#).

All visible lesions should be biopsied at Week 48. For subjects for whom Week 78 is their final visit, all visible lesions should be biopsied at Week 74. For subjects for whom the final visit is Week 96, all visible lesions should be biopsied at Week 96.

If there is a new lesion identified at evaluation, or a non-qualifying lesion that is rebiopsied and confirmed to be vulvar HSIL and HPV-16/18 positive at evaluation, a discussion will take place between the Medical Monitor and the Principal Investigator to determine if additional dosing at Week 52 is appropriate.

Pre-biopsy Vulvoscopy Finding	Minimally required procedure
No acetowhite lesion	Vulvar punch biopsy and lesion photography; biopsy should be conducted of the same qualifying lesion as study entry from the region of potentially most advanced disease based upon judgment of the Investigator; new lesions or lesions that did not qualify at baseline should be biopsied at evaluation.
Acetowhite Lesion	Vulvar punch biopsy and lesion photography; biopsy should be conducted of the same qualifying lesion as study entry from the region of potentially most advanced disease based upon judgment of the Investigator; new lesions or lesions that did not qualify at baseline should be biopsied at evaluation
Multiple acetowhite lesions	Vulvar punch biopsies and lesion photography; biopsy should be conducted of the same qualifying lesions as study entry from the region of potentially most advanced disease based upon judgment of the Investigator; new lesions or lesions that did not qualify at baseline should be biopsied at evaluation

### 3.2.1 DEFINITION OF RESPONDER AND NON-RESPONDER FOR THE PRIMARY ENDPOINT

A treatment responder is defined as a subject with no histologic evidence of vulvar HSIL and no evidence of HPV-16 or HPV-18 in vulvar tissue at evaluation and who did not receive any non-study related treatment for vulvar HSIL. A treatment non-responder is a subject with histologic evidence of vulvar HSIL or vulvar carcinoma at evaluation, or a subject with evidence of HPV-16/18 at evaluation, or a subject who received non-study related treatment for vulvar HSIL. Any case of histologically confirmed progression to carcinoma according to the PAC is considered a non-responder.

Responder and non-responder definitions ([Table 3](#)) take into account both histopathologic regression of vulvar HSIL and virologic (HPV-16/18) clearance from tissue samples since HPV persistence is an important factor in the clinical progression of HSIL.

Table 3: Definition of Responder and Non-responder for the Primary Endpoint	
Responder	Non-Responder
Subject with no histologic evidence of vulvar HSIL AND Subject with no evidence of HPV-16 or HPV-18 in vulvar tissue at evaluation AND Subject who did not receive any non-study related treatment for vulvar HSIL	Subject with histologic evidence of vulvar HSIL or vulvar carcinoma at evaluation OR Subject with evidence of HPV-16 or HPV-18 in vulvar tissue at evaluation OR Subject who received non-study related treatment for vulvar HSIL

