## 4.2 EXCLUSION CRITERIA

Subjects meeting any of the following criteria will be excluded from the study:

1. Untreated microinvasive or invasive cancer;
2. Biopsy-proven Vaginal Intraepithelial Neoplasia (VAIN) and are not undergoing medical care and/or treatment for VAIN;
3. Biopsy-proven Anal Intraepithelial Neoplasia (AIN) and are not undergoing medical care and/or treatment for AIN;
4. Biopsy-proven Cervical Intraepithelial Neoplasia (CIN) 2/3 and are not undergoing medical care and/or treatment for CIN;
5. Biopsy-proven differentiated VIN;
6. Vulvar HSIL that is not accessible for sampling by biopsy instrument;
7. Vulvar HSIL that is not of adequate size to ensure that a visible lesion remains after biopsy;

8. Treatment for genital warts within 4 weeks prior to screening;
9. Any previous treatment for vulvar HSIL (e.g. with surgery and/or imiquimod) within 4 weeks prior to screening;
10. Allergy to imiquimod 5% cream or to an inactive ingredient in imiquimod 5% cream for subjects enrolled prior to Protocol Amendment v3.0 (dated 26Mar2019);
11. Is pregnant, breastfeeding or considering becoming pregnant within 6 months following the last dose of investigational product;
12. Presence of any unresolved abnormal clinical laboratory values greater than Grade 1 per Common Terminology Criteria for Adverse Events (CTCAE) v 4.03 within 45 days prior to Day 0 or less than or equal to Grade 1 but deemed clinically significant by the Investigator;
13. Immunosuppression as a result of underlying illness or treatment including:
  - a) History of or positive serologic test for HIV at screening;
  - b) Primary immunodeficiencies;
  - c) Long term use ( $\geq 7$  days) of oral or parenteral glucocorticoids at a dose of  $\geq 20$  mg/day of prednisone equivalent (use of inhaled, nasal, otic, and ophthalmic corticosteroids are allowed);
  - d) Current or anticipated use of disease modifying doses of anti-rheumatic drugs (e.g., azathioprine, cyclophosphamide, cyclosporine, methotrexate) and biologic disease modifying drugs such as TNF- $\alpha$  inhibitors (e.g. infliximab, adalimumab or etanercept);
  - e) History of solid organ or bone marrow transplantation;
  - f) Any prior history of other clinically significant immunosuppressive or clinically diagnosed autoimmune disease that may jeopardize the safety of the subject or require therapy that would interfere with study assessments or endpoint evaluation, or otherwise impact the validity of the study results.

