## 5. STUDY TREATMENT

### 5.1 INVESTIGATIONAL PRODUCTS

The VGX-3100 drug product contains DNA plasmids for expression of HPV-16 E6/E7 (pGX3001) and HPV-18 E6/E7 (pGX3002) antigens that have been designed and constructed using proprietary synthetic consensus DNA (SynCon™) technology. The VGX-3100 formulation to be used in this study is described in [Table 9](#) and will be presented in a clear glass vial for intramuscular injection.

Imiquimod 5% is a topical cream for external use and is supplied in single-use packets containing 250 mg of cream. Each gram of the 5% cream contains 50 mg of imiquimod in an off-white oil-in-water vanishing cream base. Inactive ingredients include benzyl alcohol, cetyl alcohol, glycerin, methylparaben, oleic acid, oleyl alcohol, polysorbate 60, propylparaben, purified water, stearyl alcohol, sorbitan monostearate, white petrolatum, and xanthan gum. There are 24 single-use packets of imiquimod in one box. The product manufacturer is Perrigo, Yeruham 80500, Israel.

Imiquimod is indicated for the treatment of external genital and perianal warts/condyloma acuminata in patients 12 year old or older. Although it is not approved by the US Food and Drug Administration for the treatment of vulvar HSIL, imiquimod is currently recommended as a non-surgical, off-label treatment option for vulvar dysplasia by the American College of Obstetricians and Gynecologists (ACOG).

VGX-3100 and imiquimod will be provided by Inovio Pharmaceuticals, Inc. or its designee.

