### 6.1 BEFORE TREATMENT PROCEDURES

#### 6.1.1 SCREENING EVALUATIONS

Subjects who consent to participate and have paraffin-embedded tissue block(s) from vulvar tissue samples (formalin fixed tissue) from a previous biopsy, can have the samples sent to the central pathology lab for review by the PAC to assess eligibility. There will be a maximum allowable window of 10 weeks from the date of collection of the qualifying biopsy sample(s) (i.e. samples reviewed by PAC with HSIL consensus diagnosis), until the date of first study treatment (i.e. Day 0).

For those individuals diagnosed with vulvar HSIL by a local pathologist, where the initial biopsy tissue obtained as part of standard of care are not available or cannot be obtained within a reasonable timeframe, an additional biopsy sample should be collected during screening following the consent of the subject. The 10 week screening window begins upon collection of the biopsy sample that will be evaluated by the PAC.

Subjects must have a diagnosis of histologic vulvar HSIL confirmed by the PAC at screening, and a screening vulvar specimen test positive for HPV-16 and/or HPV-18 by PCR to be eligible for randomization into the study (provided the subject also meets other eligibility criteria). Subjects whose vulvar specimens also test positive for other HPV genotypes are not excluded as long as they have a positive result for HPV-16 and/or HPV-18.

The assessments during the screening period will determine the subjects' eligibility for the study and also their ability to comply with protocol requirements by completing all screening assessments.

The following screening evaluations will be performed within 10 weeks and up to 1 day prior to dosing on Day 0, except for the safety laboratory collections/assessments, and ECG which must be performed within 45 days prior to Day 0. All screening assessment values must be reviewed prior to study treatment.

- Signed informed consent

- Medical history/demographics, including history of prior vulvar HSIL and vulvar excisions
- Socio-Behavioral Assessment; including self-reported smoking history, self-reported exposure to second-hand smoke, self-reported alcohol intake history, contraceptive history
- Prior/concomitant medications review
- Determination of eligibility per inclusion/exclusion criteria
- Physical Exam (a full physical exam is mandatory at Screening)

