## 6.15 RESTRICTIONS

The following medications and treatments are prohibited:

- Previous treatment with imiquimod for vulvar HSIL within 4 weeks prior to screening
- Long term use ( $\geq 7$  days) of oral or parenteral glucocorticoids at a dose of  $\geq 20$  mg/day of prednisone equivalent (use of inhaled, nasal, otic and ophthalmic corticosteroids are allowed)
- Disease modifying doses of anti-rheumatic drugs (e.g., azathioprine, cyclophosphamide, cyclosporine, methotrexate), and biologic disease modifying drugs such as TNF- $\alpha$  inhibitors (e.g. infliximab, adalimumab or etanercept) at screening and throughout the study
- Administration of any non-study related, non-live vaccine within 2 weeks of any study treatment or within 4 weeks of any study treatment for any non-study related live vaccine
- Blood thinners/Anticoagulants within 2 weeks of any study treatment

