### 8.3 SAMPLE SIZE/POWER

A sample of 36 subjects will be randomized to receive either 6 mg VGX-3100 or 6 mg VGX-3100 plus imiquimod, IM followed by EP in a 2:1 ratio. This sample size provides 80% power to declare each study group superior to historical control with a one-sided

0.025 type 1 error level for each hypothesis, assuming the true proportion of subjects who achieve the primary endpoint is 20% and 28% for the respective treatment arms and 2% for the historical control, and that 90% are evaluable at Week 48 from randomization.

The Version 3.0 protocol amendment halts enrollment of the VGX-3100 with topical imiquimod study group. All subjects who have already been enrolled into the VGX-3100 with imiquimod study group will continue with all study visits per protocol, but no further participants will be enrolled into this group.

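### The responder tables disqualify outside treatment by its label (for vulvar HSIL) and give no time window, so clearance after non-study imiquimod or other vulvar treatment given for warts would count for VGX-3100

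*Protocol*

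**What the plan says.** **Responder rule.** In Section 3.2.1, Table 3, a responder must have no histologic HSIL, no HPV-16/18 in vulvar tissue, and be a "Subject who did not receive any non-study related treatment for vulvar HSIL". Section 3.2.2 attaches the same condition to every secondary and exploratory responder definition (Tables 4 to 8). No table gives a start or end date for it, and none mentions treatment of the vulva for another indication.

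**Imiquimod.** Section 1.1.14 states that randomised trials have shown topical imiquimod to work in vulvar HSIL. Section 5.1 gives its licensed use: "Imiquimod is indicated for the treatment of external genital and perianal warts/condyloma acuminata".

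**What is restricted.** Exclusion 8 bars wart treatment only in the 4 weeks before screening. The prohibited list in Section 6.15 names imiquimod once: "Previous treatment with imiquimod for vulvar HSIL within 4 weeks prior to screening". Section 6.14 otherwise leaves necessary medication to the Investigator's discretion.

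**Non-vulvar sites.** Exclusions 2 to 4 bar biopsy-proven VAIN, AIN and CIN 2/3 only when the woman is not under care or treatment. For AIN the wording is: "Biopsy-proven Anal Intraepithelial Neoplasia (AIN) and are not undergoing medical care and/or treatment for AIN". Exploratory endpoint 5 (Section 2.3) counts HPV-16/18 clearance "from non-vulvar anatomic locations without surgical intervention".

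**Prior HSIL treatment.** Exclusion 9 bars "Any previous treatment for vulvar HSIL (e.g. with surgery and/or imiquimod) within 4 weeks prior to screening". Section 6.1.1 lets the qualifying biopsy be up to 10 weeks old at Day 0.

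**The concern.** Each arm is compared with a fixed 2% taken as the untreated rate (Section 8.9), with no concurrent control that could absorb responses due to another therapy. A rule for outside treatment therefore has to catch anything that could clear the sampled tissue. This one asks what the treatment was prescribed for.

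Take a woman on VGX-3100 alone who is given imiquimod for vulvar warts between Day 0 and Week 48. She breaches no listed restriction, and if her biopsies are clear she is a responder. Yet the protocol regards imiquimod as active enough to be the add-on in the other arm. Ablative or excisional wart treatment on the vulva passes the rule in the same way. Residual condyloma at evaluation does not fail her either, because the synopsis counts condyloma as absence of HSIL.

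Endpoint 5 has a related gap. Women already under non-surgical treatment for VAIN, AIN or CIN can enter, and clearance at that site after such treatment is counted because only surgery disqualifies.

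**Working it through.** **Inputs.** 24 and 12 women planned (Section 3); 90% evaluable; true rates 20% and 28% against 2%; a one-sided "0.025 type 1 error level for each hypothesis" (Section 8.3). Section 8.9 requires one-sided exact p < 0.025 and a Clopper-Pearson 95% lower bound above 0.02.

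**Reproducing the planned power.** Evaluable numbers are 24 × 0.9 = 21.6 and 12 × 0.9 = 10.8. The critical count r is the smallest with P(X ≥ r | n, 0.02) < 0.025.

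| Arm | n | r | Exact alpha | Power |
|---|---|---|---|---|
| VGX-3100 alone (20%) | 21 | 3 | 0.0081 | 82.1% |
| VGX-3100 alone (20%) | 22 | 3 | 0.0093 | 84.6% |
| With imiquimod (28%) | 10 | 2 | 0.0162 | 81.7% |
| With imiquimod (28%) | 11 | 2 | 0.0195 | 85.8% |

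The stated 80% holds as at least 80% and is not in dispute.

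**What one responder does.** For n = 22, P(X ≥ r) = 1 − Σ(k<r) C(22,k) × 0.02^k × 0.98^(22−k).

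- 2/22: p = 0.0710, lower bound 1.12%. Not superior.
- 3/22: p = 0.0093, lower bound 2.91%. Superior.

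For n = 11, 1/11 gives p = 0.199; 2/11 gives p = 0.0195 and a lower bound of 2.28%.

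**Illustration under assumptions.** The documents give neither the share f of women with uncounted treatment nor their response rate q on the composite endpoint, so both are assumed here. If VGX-3100 did nothing, the response probability would be 0.02(1 − f) + fq. The chance of at least 3 responders in 22 is then:

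| f | q = 0.2 | q = 0.3 | q = 0.5 |
|---|---|---|---|
| 5% | 0.0249 | 0.0374 | 0.0703 |
| 10% | 0.0493 | 0.0863 | 0.1855 |
| 20% | 0.1225 | 0.2318 | 0.4781 |

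The exact alpha without such treatment is 0.0093.

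**Power if those women are counted as non-responders.** The response probability becomes p1(1 − f).

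| f | n = 22, p1 = 0.20 | n = 11, p1 = 0.28 |
|---|---|---|
| 0 | 84.6% | 85.8% |
| 5% | 81.7% | 83.4% |
| 10% | 78.5% | 80.7% |
| 20% | 70.7% | 74.4% |

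**The case against.** **Frequency and mechanism.** A misattributed response needs a chain of events: warts on study, imiquimod or another vulvar treatment for them, action on the qualifying lesion, and clearance of both HSIL and HPV-16/18 that would not otherwise have occurred. No step has a documented frequency, and Week 48 biopsies target the qualifying lesion and all visible lesions rather than wart sites elsewhere. That one extra responder tips 2/22 to 3/22 is true of any misclassification in an arm this small. All of this stands. It limits how strongly the point can be put, but it does not close the gap in the definition.

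**Treatment after a historical biopsy.** A reader might infer that HSIL treatment given between an old qualifying biopsy and Day 0 is credited to VGX-3100. The text does not support that. Such treatment is for vulvar HSIL, and Table 3 says any, without dates, so read literally she is a non-responder. Lesion visibility and demarcation at entry, with Day 0 vulvoscopy and photography, are further partial safeguards, although no histology is repeated at Day 0. The defect is the missing window. The literal reading would also fail women treated earlier for recurrent disease, who are a planned stratum.

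**VAIN, AIN and CIN treatment.** A reader might infer that this inflates the primary endpoint. The documents nowhere say that treatment at those sites acts on vulvar lesions. Nor do they say how many women would be on treatment; being under care need not mean being treated. This part concerns a descriptive exploratory endpoint only.

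**An over-wide remedy.** Failing every woman with any vulvar excision or topical product would contradict Sections 2.1 and 6.2.10, under which the evaluation tissue may itself come from excision, and would catch creams with no bearing on HSIL. This objection is right and shapes the fix.

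**Conclusion.** The point holds in a limited form. As written, Tables 3 to 8 let clearance after non-study imiquimod, or after ablative or excisional treatment of the vulva for another indication, count as response to VGX-3100, and no other section prevents it. At the planned size one such woman could decide superiority for VGX-3100 alone (threshold 3 of 21 or 22); for the combination the threshold is 2 of 10 or 11. How likely this is cannot be derived from the protocol: the false-positive figures rest wholly on assumed f and q and are not estimates. The undated condition also leaves earlier HSIL treatment open to two readings. The endpoint 5 gap is real but separate and descriptive.

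**What to change.** Change the analysis definitions only.

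- **Tables 3 to 8, and the matching synopsis text:** count as a non-responder any woman who, from her qualifying biopsy up to but not including the evaluation specimen, received non-study imiquimod or another HPV- or lesion-directed topical, ablative or excisional treatment on the vulva, whatever the recorded indication. Exempt assigned study imiquimod, diagnostic biopsies, the evaluation biopsy or excision that the protocol permits, and unrelated topical products.
- **Exclusion 9:** no change is needed. The window settles how treatment between a historical qualifying biopsy and Day 0 is counted, and stops earlier treatment for recurrent disease from failing a woman.
- **Exploratory endpoint 5 (synopsis and Section 2.3):** replace the surgery-only condition with one requiring no surgical, ablative or lesion-directed topical treatment at that site.

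**Cost.** Wording, with no new visit or test. Section 6.14 already collects medications with their indication, and procedures, from 8 weeks before the screening biopsy. It does not list site of application, so a few topical records may need a query. A few women may move to non-responder. On the assumptions above, power for VGX-3100 alone falls from 84.6% to 81.7% if 5% are reclassified and to 78.5% if 10% are. The loss is small only if such treatment is uncommon.
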